6.4 STUDY INTERVENTION COMPLIANCE

For the assessment of compliance, we will take the following measures:

- **Visit to assess compliance (Visit 3):** We will assess compliance during Visit 3, which will take place in between Visits 2 (baseline and assessment of acute effects) and 4 (assessment of chronic effects) of the study. During this Visit, blood will be drawn for the assessment of blood BHB levels. In addition, we will assess their compliance logs (see below).
- **Phone calls:** We will place phone calls once between Visits 2, 3 and once between Visits 3, 4. Potential concerns and/or questions will be discussed in the calls and symptoms/AEs will be elicited.
- **Logs of supplement intake:** Participants will be asked to keep a log on which they will report the timing of each dose of the drink they take. Keeping a log will reinforce their commitment to take the supplement as instructed properly. They will bring in these logs during Visits 3 and 4.

6.5 CONCOMITANT THERAPY

For this protocol, both prescription medications (defined as a medication that can be prescribed only by a properly authorized/licensed clinician) and over-the-counter medications and supplements are potentially important modifiers of the effect of the interventions. Therefore, concomitant prescription medications, over-the-counter medications and supplements will be recorded during all four planned Visits.

Excluded concomitant compounds will be ketogenic supplements such Medium Chain Triglycerides, Coconut oil, Ketone Salts or any other supplement advertised as “ketogenic”.

We do not expect any interactions of any of the allowed concomitant medications with the study intervention. Also, allowed concomitant interventions are not expected to affect any of the study outcomes.

7 STUDY INTERVENTION DISCONTINUATION AND PARTICIPANT DISCONTINUATION/WITHDRAWAL

7.1 DISCONTINUATION OF STUDY INTERVENTION

Discontinuation from study’s intervention means discontinuation from the study. If a clinically significant finding is identified (including, but not limited to changes from baseline) after enrollment, the PI will determine if any change in participant management is needed. Any new clinically relevant finding will be reported as an adverse event (AE).

Participants are free to discontinue the study intervention at any time upon request.

7.2 PARTICIPANT DISCONTINUATION/WITHDRAWAL FROM THE STUDY

Participants are free to withdraw from participation in the study at any time upon request.

The PI may discontinue a participant from the study for the following reasons:

- Screen failure.
- The participant meets an exclusion criterion (either newly developed or not previously recognized) that precludes further study participation
- The participant has an adverse event (AE), including clinical signs and/or symptoms, laboratory abnormality, or other medical condition or situation, such that continued participation in the study would not be in the best interest of the participant, at the judgment of the PI.
- The participant manifests significant study non-compliance (e.g. the participant was deemed eligible but didn't show for any Visit. Also, if the participant's log of supplement intake during Visit 3 shows multiple skipped doses or skipped days of intervention).
- The participant has any condition, which in the opinion of the PI, could interfere with the study procedures.
- MRI will be stopped at the request of the participant as a result of claustrophobia or problems associated with lying in the scanner for any length of time. If MRS measures for BHB (primary outcome) cannot be obtained, this will constitute discontinuation of the participation.
- Death.

Participants that are discontinued/withdrawn from the study will be replaced by new participants. The reason for participant discontinuation or withdrawal from the study will be recorded on the medical record.

7.3 LOST TO FOLLOW-UP

A participant will be considered lost to follow-up if they do not present in one or more Visits. The following actions will be taken if a participant fails to return to the clinic for a required study Visit:

- The site will attempt to contact the participant and reschedule the missed Visit. Specifically, for Visit 4, which is the final Visit, we will attempt to reschedule it within 3 days from the original date. For Visit 1 (baseline Visit) and Visit 2 (initiation Visit), the participants can reschedule according to their availability. For Visit 3 (compliance Visit), they should reschedule within the 3 next days.
- Before a participant is deemed lost to follow-up, the investigator or designee will make every effort to regain contact with the participant (where possible, place 3 telephone calls and, if necessary, a certified letter to the participant's last known mailing address). These contact attempts should be documented in the participant's medical record.
- Should the participant continue to be unreachable, she/he will be considered to have withdrawn from the study with a primary reason of "lost to follow-up".

8 STUDY ASSESSMENTS AND PROCEDURES

8.1 SCREENING PROCEDURES

The screening procedures will involve two phases: first we will contact individuals who are interested in participating in the study via phone and pre-screen them according to their self-report of meeting inclusion/exclusion criteria. Next, if not excluded via phone pre-screening, we will screen them during Visit 1 to ascertain inclusion/exclusion criteria. No screening procedures will take place until the subject has provided informed consent during Visit 1. During the informed consent, participants will be given the option to participate in the additional thigh muscle MRS study. If they opt to not participate in it, they will still be eligible to complete the rest of the procedures. The determination of eligibility will involve the next procedures:

- Nursing Assessment
- Assessment of vital signs and anthropometric measures (waist circumference, etc.),
- Blood drawing for screening clinical labs: complete blood count (CBC) with automatic differential, lipid panel (including HDL and TGs, which are part of the definition of MetS), complete metabolic panel (including glucose, which is part of the definition of MetS), HgbA1c, and fasting insulin, HIV, HBV, HCV.
- History and Physical
- Urine test for drugs
- Urine pregnancy. Pregnancy tests will not be done on post-menopausal women defined as one of the below criteria:
 - a. prior bilateral oophorectomy
 - b. Amenorrhea for 12 months or more
- Cognitive assessment for eligibility (CDR, MOCA)

8.2 EFFICACY ASSESSMENTS

8.2.1 Clinical Evaluations

No clinical evaluations are meant to assess efficacy.

8.2.2 Neuropsychological Assessment

Cognitive testing will be administered by a study investigator during the screening, baseline and final visits (Visits 2 and 4). Screening cognitive testing will consist of screening tests that are commonly used to ascertain normal cognitive status: participant-informed Clinical Dementia Rating (CDR) scale (global score = 0) and Montreal Cognitive Assessment (MoCA) (≥ 26). For deriving efficacy measures, we will use a battery modeled after the preclinical Alzheimer cognitive composite (PACC [57](#)), which includes the Free and Cued Selective Reminding Task (FSCRT) for list learning, the Logical Memory task for episodic memory, the Digit-Symbol task for timed executive function, the MoCA as a global cognitive measure, and an overall Z-transformed composite score. In addition, attention, episodic memory, working memory, language/fluency, and executive function, and their composite score will be assessed via the NIH Toolbox (www.nihtoolbox.org [58](#)); a comprehensive, psychometrically sound, and well-validated computerized testing battery that reliably and uniformly assesses cognitive function. Cognitive

testing will take place before the supplement intake at Visit 2 (baseline) and ~3 hours after supplement intake at Visit 4 to assess acute on chronic effects.

8.2.3 Magnetic Resonance Spectroscopy (MRS)/Magnetic Resonance Imaging (MRI):

The 3T Philips MRI system used in the NIA Clinical research Unit is an FDA-approved clinical device which we use within its marketed purposed for our research. Some of the MRI sequences used in this study require that the 3T Philips scanner be run in “Research Mode” using research pulse sequences, all of which operate within FDA guidelines, under the International Electrotechnical Commission (IEC) 60601-2-33, First Level-Controlled Operating Mode. The IEC/FDA define operating mode limits on MRI studies for RF heating (Specific Absorption Rate) and Time-varying magnetic field gradients (dB/dt). The research sequences can be classified as NSR devices because normal, healthy volunteers are used in this study and these pulse sequences adhere to the FDA/IDE safety standards. Therefore, there is no significant risk to the subject from these research pulse sequences. Furthermore, research software is used to process and analyze the data. Since the processing does not add any increased risk to the healthy volunteers in this study, it is also classified as NSR. The research pulse sequences and research software will not be used for diagnosis or clinical decision making.

This investigational device, as utilized in this study, is considered a Non-Significant Risk (NSR) device per 21 CFR 812.2(b)(1). The NSR classification was established as the device **does not meet** the following criteria for a Significant Risk Device (21 CFR 812(m)), i.e., a device that:

1. Is intended as an implant and presents a potential for serious risk to the health, safety, or welfare of a subject;
2. Is purported or represented to be for a use in supporting or sustaining human life and presents a potential for serious risk to the health, safety, or welfare of a subject;
3. Is for a use of substantial importance in diagnosing, curing, mitigating, or treating disease, or otherwise preventing impairment of human health and presents a potential for serious risk to the health, safety, or welfare of a subject; or
4. Otherwise presents a potential for serious risk to the health, safety or welfare of a subject

A standard MRI safety screen is administered prior to participation in any studies involving MRI or MRS to verify that participants can safely enter the magnetic area.

a) Brain:

Structural brain MRI (3D T1 sequence MPRAGE for voxel placement and partial volume correction, T2, DWI, and FLAIR to provide clinical read) and resting state fMRI to associate with MRS metabolites as previously done [59](#).

Single voxel ¹H-MRS data will be acquired using a Philips 3T whole-body MR scanner equipped with an 8-channel SENSE head coil. A volume of interest of 25 × 18 × 20 mm³ will be placed at midline over the bilateral posteromedial cortex (PMC). To accurately measure brain Glucose concentration, we will acquire a two-dimensional j-resolved spectrum using a J-PRESS sequence with maximum-echo sampling [60](#). This method acquires a dynamic series of PRESS spectra incrementing the echo time to encode J-modulations in the second (indirect) dimension; this

additional dimension permits the discrimination and quantification of resonances that overlap in the directly detected chemical shift direction but have different J couplings. The echo times in this study are to be incremented from 31 ms to 229 ms using 100 echo steps with a step size of 2 ms. JPRESS acquisition parameters consist of a repetition time = 1600 ms, eight averages per echo time, bandwidth in the direct dimension = 2 kHz, 1024 sample points, for a total scan duration of 21 min and 20 s. Line widths for the water resonance are monitored for intra-subject scan reliability and have been previously observed at a stable (mean \pm SD) 7.3 ± 1.7 Hz.

A PRESS sequence with non-suppressed water signal reference in the same region will be acquired to obtain measurements of the ketone bodies β -hydroxybutyrate, aceto-acetate, and acetone [34,61](#). A reliable modified basis set including these ketone metabolites was acquired via personal communication from [name] in July of 2019. PRESS parameters are: TE = 35 ms, TR = 2000 ms, 256 averages, direct dimension bandwidth = 2 kHz, and 2048 sample points. Data will be processed with LCModel [62](#).

Total scanning time will be ~45 minutes for each brain-scanning session. In both Visits 2 and 4, two brain-scanning sessions will take place, first, during fasting, then ~ 90 minutes after supplement intake, to assess both baseline and changes after the administration of the KE drink.

b) Optional thigh Muscle 31P MRS:

We will implement a moderate leg exercise protocol combined with 31P MRS to assess muscle bioenergetic capacity. The exercise protocol consists of knee extension performed while the subject is lying supine in the MRI scanner. The average duration of exercise will be 30 seconds, based on two criteria as determined by real-time evaluation of 31P spectra: (i) reduction in phosphocreatine (PCr) peak height by 30% to 70% compared with initial values, and (ii) avoidance of significant intracellular muscle acidification, defined as pH lower than 6.8.

All spectra will be obtained using a pulse-acquire sequence, with a 6-second duration for each acquisition. Acquisition will be initiated 60 seconds before exercise and continued throughout the exercise period, and then for 360 seconds during the post-exercise recovery period. Thus, a total of 75 spectra will be obtained for each participant's exercise protocol. The information content of these 31P spectra includes intramuscular pH, and PCr and ATP levels relative to their resting level. pH is expected to decline during exercise and recover post-exercise, ATP is expected to remain constant for this moderate exercise protocol, and PCr is expected to decline during exercise and recover post-exercise. The time constant of this post-exercise PCr recovery will be obtained through use of a mono-exponential fit of the recovery data and will be expressed as τ_{PCr} , in units of seconds. This time constant is inversely proportional to maximum muscle oxidative capacity, with a slower recovery, indicated by a larger τ_{PCr} , reflecting lower oxidative capacity.

Total scanning time (including set up) will be ~ 45 min for each muscle 31P MRS session. In Visit 2 and 4, two muscle-scanning sessions will take place, first, during fasting, then ~ 1.5 hours after the administration of the KE drink.

8.2.4 Compliance Assessments

In addition to including a dedicated compliance visit (Visit 3), we will communicate with participants via phone call, once between Visits 2, 3 and once between Visits 3, 4. Participants will also be advised to keep a log of the times of taking each dose. They will be asked to bring the Log in for review on Visits 3 and 4.

8.2.5 Biospecimen Evaluations**Biological specimen collection**

Clinical labs will be sent to CLIA Medstar Harbor Hospital and results will be acquired in real time. All other labs will be done for research purposes and sample processing (e.g. to derive EVs) and measurements (e.g. serum BHB, plasma EV biomarkers) will be conducted in batches by research Lab personnel at the NIA Biomedical Research Center. HgbA1c will be performed by the NIA Harbor Lab.

Venous blood draws and urine collection during Visit 1 (Screening Visit):

Up to 40 ml of blood will be drawn for the assessment of screening clinical labs including CBC with differential, Comprehensive Metabolic Panel including fasting glucose, Lipids panel (TGs, total cholesterol, LDL, HDL), HgbA1c, and fasting insulin, HBV, HCV and HIV. All screening blood draws will be performed after fasting for 12 hours. All of these tests will be conducted by the CLIA Medstar Harbor Hospital lab except for the HgbA1c which will be performed by the NIA Harbor Lab.

Urine will also be collected to test for pregnancy in women with child-bearing potential. See section 8.1.

Venous blood draws and stool/urine samples during Visit 2 (Baseline Visit):

Up to 40 ml of blood will be collected in (i) serum separator tubes for eventual measurement of β -hydroxybutyrate (BHB) by BRC research personnel; and (ii) EDTA tubes for eventual EV isolation and biomarkers by BRC research personnel. Up to 35 ml will be collected before the first supplement dose and ~5 ml after ~ 60-75 minutes from it. Urine will also be collected to test for pregnancy in women with child-bearing potential. See section 8.1. Stool samples (brought from home) will also be collected for assessment of gut microbiome before the first dose. The stool samples should be collected at home, no more than 24 hours before this Visit. The participants will be provided supplies and instructions to obtain the stool sample. Urine will be collected throughout the Visit (over ~ 8 hours), for measurement of urine BHB. Urine pregnancy test will be also performed in women with child-bearing potential. See section 8.1.

Venous blood draws during Visit 3 (Compliance Visit):

Up to 40 ml of blood will be collected in (i) serum separator tubes for eventual measurement of β -hydroxybutyrate (BHB) by BRC research personnel; and (ii) EDTA tubes for eventual EV isolation and biomarkers by BRC research personnel. Up to 35 ml will be collected before the supplement dose and ~5 ml after ~ 60-75 minutes from it. Urine will also be collected to test for pregnancy in women with child-bearing potential. See section 8.1. Urine pregnancy test will be also performed in women with child-bearing potential. See section 8.1.

Venous blood draws and stool/urine sample during Visit 4 (Outcome Visit):

Up to 55 ml of blood will be collected for (i) clinical labs, including CBC with differential, Comprehensive Metabolic Panel including fasting glucose, Lipids panel (TGs, total cholesterol, LDL, HDL), HgbA1c (will be performed by the NIA Harbor Lab), and fasting insulin (will be conducted by the Medstar Harbor Hospital lab); and (ii) serum separator tubes for eventual measurement of β -hydroxybutyrate (BHB) by BRC research personnel; (iii) EDTA tubes will be drawn for eventual EV isolation and biomarkers by BRC research personnel. Up to 50 ml will be

Abbreviated Title: *Oral Ketone Ester effects on brain function*

Version Date: 10/29/2024

collected before the supplement dose and ~5 ml after ~ 60-75 minutes from it. Urine will also be collected to test for pregnancy in women with child-bearing potential. See section 8.1.

Stool samples (brought from home) will also be collected for assessment of gut microbiome after the supplement intake. The stool samples will be collected at home, no more than 24 hours before Visit 2 and 4. Urine will be collected throughout the Visit (over ~ 8 hours), for measurement of urine BHB. Urine pregnancy test will be also performed in women with child-bearing potential. See section 8.1.

Venous blood draws during Visit 5

Up to 10 ml of blood will be collected for DNA collection to genotype subjects for the Apolipoprotein E (*APOE*) (the most significant genetic risk factor for AD) and the solute carrier family 16 member 7 (*SLC16A7*) genes; and potentially polymorphisms for other genes and other genetic factors.

Storage

The subject's stored samples will be labeled with a code (such as letters and numbers) that only the study Investigators can link to the subject. Any identifying information about the subject will be kept confidential to the extent permitted by law. Samples acquired during this study will be tracked using the NIA Biological Sample Inventory system following NIH guidelines.

Samples of the subject's blood and stool will be kept at the National Institutes on Aging, NIH Core Lab or one of our contract facilities; a subset of these samples may be retained at the Laboratory of Clinical Investigation (LCI) at the PI's freezers. The subjects' research samples will be stored with a confidential code and will be processed in batches at later times (not in real times). If consent for sharing was obtained in the original consent form, samples may be released to other physicians and scientists who are not listed as collaborators. The PI on this protocol will decide which co-investigators and collaborating researchers may receive samples. The subjects' samples may be used in their research only if the research has been approved by an Institutional Review Board (IRB). We will code the blood and stool samples and keep the subject's identity confidential. We will retain a code list that enables us to link the clinical information and results on each sample to the subject.

We will code the blood that will keep the subject's identity confidential. We will retain a code list that enables us to link the clinical information and results on each sample to the subject. DNA extraction from peripheral blood mononuclear cells (PBMCs) will take place for *APOE* and *SLC16A7* genotyping and, potentially, additional genetic factors. We will not conduct Whole Genome (WGS) or Whole Exome Sequencing (WES). DNA samples will be stored at the NIA Core Lab.

Access to research samples will be limited using either a locked room or a locked freezer. Samples and data will be stored using codes assigned by the investigators or their assigned designee(s). Data will be kept in password-protected computers. Only investigators or their designee(s) will have access to the samples and data.

At the Study Termination (after data analysis), samples and data will, after IRB approval, be transferred to another existing protocol or a repository protocol.

Data and sample sharing plan

Data and samples may be shared with collaborating laboratories at NIH or outside of NIH if consent for sharing was obtained in the original consent form. Samples/data that we may share in the future include biological specimens (blood and stool), MRI images and cognitive test results. If we wish to share samples in the future, samples and data will be stripped of identifiers and may be coded (“de-identified”) or unlinked from an identifying code (“anonymized”). When coded data is shared, the key to the code will not be provided to collaborators but will remain at NIH. Data and samples may be shared with investigators and institutions with an FWA or operating under the Declaration of Helsinki (DoH) after prospective IRB approval. Required approvals from the collaborating institution will be obtained and materials will be shipped in accordance with NIH and federal regulations. No NIH or external collaborators that may receive samples have been identified at this time.

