1.2 SCHEMA

[figure not shown]
**Pre-Visit phone call/
Visit 1**
Screening Visit

Visit 2
Day 1 on
supplement

Abbreviated Title: Oral Ketone Ester effects on brain function

Version Date: 10/29/2024

Note: During the 28 ± 3-day period, participants will self-administer the intervention at home, three times per day. On Visits 2, Visit 3 and Visit 4, the first dose of the daily intervention will be given at the NIA Clinical Unit, where the Visits will take place.

Visit 5 (Follow-up visit)

Informed consent and blood draw for DNA collection.

Abbreviated Title: Oral Ketone Ester effects on brain function
Version Date: 10/29/2024

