1.3 SCHEDULE OF ACTIVITIES (SOA)

Procedure	Pre-Visit phone Screen	Visit 1	Visit 2	Visit 3	Visit 4	Visit 5
		Screening	Baseline assessments – first dose – acute effects assessments	Compliance Assessment	Last dose. Chronic effects assessments	
Timing			Within 28 days of V1 Day 1 on supplement	Day 14 (+/-3 days) on supplement	Day 28 (+/-3 days) on supplement	
Informed Consent		X				X
Screening of Inclusion/Exclusion Criteria	X	X				
Demographics		X				
Medical History		X				
Review of concomitant medications		X	X	X	X	

Abbreviated Title: Oral Ketone Ester effects on brain function
Version Date: 10/29/2024

Physical Exam		X			X	
Vital signs		X	X	X	X	
Nursing assessment		X	X	X	X	
Anthropometric measures [Height (cm), Weight (kg), waist circumference (cm or in)] *Height to be measured during V1 only. Weight and waist circumference to be measured during V1 and V4.		X			X	
Blood draw for screening clinical labs: See section 8.2.5		X (fasting)				
Blood draw for clinical labs and EV biomarkers. See section 8.2.5			X (fasting/before supplement)	X (fasting/before supplement)	X (fasting/before supplement)	
Blood draw for DNA collection (for genetic studies): See section 8.2.5						X
Serum β -hydroxybutyrate			X (fasting and ~60 min after supplement)	X (fasting and ~60 min after supplement)	X (fasting and ~60 min after supplement)	
Stool samples			X (within 24 h before the visit)		X (within 24 h before the visit)	
Urine BHB			X (collected during the visit)		X (collected during the visit)	

Abbreviated Title: Oral Ketone Ester effects on brain function
Version Date: 10/29/2024

Urine drug screen		X				
Urine Pregnancy test		X	X	X	X	
Cognitive assessment for eligibility (CDR, MOCA)		X				
Randomization (after eligibility determined) by NIA Pharmacist		X				
Ketone Ester or Placebo dispensed by NIA pharmacist			X (first of three daily doses received in-house)	X (first of three daily doses received in-house)	X first of three daily doses received in-house)	
Self-administration of Ketone Ester or Placebo x 3 times per day			Throughout the 28-day period			
MRI/MRS Brain			X (before and ~75 min after supplement)		X (before and ~75 min after supplement)	
Optional Thigh MRS			X (before after supplement)		X (before and after supplement)	
Outcome cognitive testing			X (before the supplement)		X (~ 2.5 h after the supplement)	
Review compliance logs of drinks				X	X	
Modified Credibility/Expectancy Questionnaire				X	X	

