watches, coins, jewelry, and credit cards) will be removed before entering the MRI scan room. Participants with history of surgeries, implanted devices, etc. will be asked to provide us with surgical reports mentioning the type of the clips, prostheses, etc. used. Every effort will be made to establish the MR compatibility or incompatibility of these implants, according to the safety standards of the NIA 3T MRI center, including obtaining reports by manufacturing companies for MR compatibility. The research staff will evaluate each person with a less severe history of claustrophobia on a case-by-case basis.

Regarding minor discomforts, rapidly changing magnetic fields of gradient coils, which are frequently used in research, can induce electrical fields in human tissue. This can result in stimulation of peripheral nerves and on rare occasions the participant may experience a mild sensation such as a light vibration, muscle twitching or poking of the skin with the effects varying from person to person. It has no lasting effects on the nervous system and the test will be stopped when the participant reports the symptoms to the MRI technician. The loud sounds (> 120 dB) emitted by the MRI machine during scanning require earplugs but may cause mild acoustic discomfort.

Incidental findings on MRI that are non-life threatening and do not requiring further medically indicated diagnostic testing or treatment may occur in up to 5% of the participants.

Exercise Protocol for thigh muscle 31P MRS (Optional): There is a risk that an exercise procedure may cause fatigue, muscle cramping and/or strain. Participants will be asked to report any pain or discomfort as they complete the procedure(s) and based on the participant's response, the procedure may be modified or terminated by the researcher.

- **Genetic testing (genotyping for APOE and other modulatory genes; DNA methylation):** The DNA analysis that will be done as part of this study is for research purposes only.

The primary risk associated with genetic testing in this study relates to the potential for a breach of confidentiality. In the event of a breach, genetic information could be misused, leading to issues such as discrimination related to employment and/or life and/or health insurance. While such incidents are rare, they are possible. Additionally, access to genetic information could cause psychological distress or tension within families if a breach were to occur.

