3 OBJECTIVES AND ENDPOINTS

OBJECTIVES	ENDPOINTS	JUSTIFICATION FOR ENDPOINTS
Primary		
To investigate the change in brain concentration of BHB, using brain MRS, after 28 days of supplementation with the KE drinks compared to baseline and placebo.	To detect with brain MRS, a significant change in the concentration of BHB, after 28 days of supplementation with KE drinks compared to baseline and placebo.	A previous study on a different ketogenic intervention (MCTs) given to individuals with AD, showed that the combined AcAc and BHB CMR measured globally or at specific

OBJECTIVES	ENDPOINTS	JUSTIFICATION FOR ENDPOINTS
		regions (frontal lobe, parietal lobe, temporal lobe, occipital lobe, cingulate cortex, subcortical regions) with PET scan, was significantly increased. With this ketogenic intervention there was also improvement in only 3 out of the 23 different cognitive tests ⁶ . We expect to demonstrate a change in brain BHB with KE using brain MRS, a technique that measures concentration rather than CMR.
Secondary		
To assess whether genetic factors modulate the response to the KE supplement.	To assess whether genetic factors modulate the response to the KE supplement.	In a previous randomized clinical trial of 5:2 Intermittent Fasting versus Healthy Living diet in older individuals with insulin resistance, we showed that the diets had differential effects on induction of peripheral ketosis based on genetic polymorphisms for the SLC16A7 and APOE genes. ³⁵ We expect to find similar differential effects on induction of peripheral and, by extension, brain ketosis in response to the KE supplement.
Exploratory		
i) (a) To investigate the acute effects (single dose) of KE drink on brain BHB measured with brain MRS, compared to	i) (a) To detect with brain MRS, a significant change in the concentration of BHB, acutely after single dose of KE drink, compared to	i) (a) and (b): We have shown higher Glucose/Creatine and Lactate/Creatine

OBJECTIVES	ENDPOINTS	JUSTIFICATION FOR ENDPOINTS

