9.4.3 Analysis of the Secondary Endpoint(s)

To assess whether genetic factors modulate the response to the KE supplement, in the repeated-measures mixed models, we will include the *APOE* $\epsilon 4$ carrier status ($\epsilon 4$ carriers, $\epsilon 4$ non-carriers), the *SLC16A7*, and potentially other polymorphisms, as additional fixed effect factors and their interactions with “Group” and “Time”.

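### The only DNA sample for the sole secondary endpoint is drawn at an undated, separately consented visit after treatment, so dosed participants who stop early or do not return have no genotype

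*Protocol*

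**What the plan says.** Protocol section 3 gives one secondary endpoint: "To assess whether genetic factors modulate the response to the KE supplement". Section 9.4.3 and the matching SAP section add APOE e4 status, SLC16A7 and possibly other polymorphisms to the mixed models, with their interactions with Group and Time.

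The DNA draw appears in three places, all at Visit 5:

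- The Schedule of Activities row "Blood draw for DNA collection (for genetic studies): See section 8.2.5" has a single mark, in the Visit 5 column.
- Section 8.2.5 says, under Visit 5, "Up to 10 ml of blood will be collected for DNA collection to genotype subjects for the Apolipoprotein E".
- The specimen table in section 8.2.6 lists about 8 ml at Visit 5. Its other row gives study days; this one does not.

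The EDTA blood from Visits 2 to 4 is assigned to extracellular vesicle work, and no DNA use is planned for it. The schema describes Visit 5 as "Informed consent and blood draw for DNA collection", so it carries its own consent. The Schedule marks Visit 4 as the last dose.

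On missed visits, section 7.3 says "A participant will be considered lost to follow-up if they do not present in one or more Visits", and section 7.2 says "Participants that are discontinued/withdrawn from the study will be replaced by new participants". Section 7.3 has rescheduling rules for Visits 1 to 4 only and treats Visit 4 as the final one.

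**The concern.** A mixed model can use a participant with some missing outcome values. It cannot use a participant whose genotype, a fixed effect in the model, is missing: that person drops out of the genetic analysis altogether. Under this plan, having a genotype depends on staying in the study to the end of treatment, coming back at an unspecified later time and signing a further consent. All of that happens after randomisation and after exposure.

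Two things are at stake. One is precision, in an interaction test that is already weak at 50 participants. The other is the comparison itself: among those who return, the two arms are no longer guaranteed to be the groups that randomisation made. Return could depend on tolerability or perceived benefit, which could differ by arm. Neither document gives an analysis set or a missing-data rule for participants without DNA.

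**Working it through.** **1. The plan's own figure.** Section 9.2 gives 25 per arm for d = 0.80, two-sided alpha 0.05 and power 0.80. By the normal approximation, n = 2(1.960 + 0.842)²/0.80² = 24.5, so 25 per arm, with power 0.807. By the t test, n = 25.5 (26 per arm), and power at 25 is 0.791. The figure reproduces. It is for the primary endpoint; no figure is given for the genetic endpoint or for Visit 5 attendance.

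**2. Is Visit 5 dated anywhere?** Even with the Schedule's timing row set aside, the synopsis, schema, section 8.2.5 and specimen table give no day or window. The participant duration of 59 days is 28 + 31 (screening window plus 28 + 3 days on supplement), which leaves Visit 5 out. Section 6.5 counts four planned visits.

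**3. Who has MRS data but no genotype?**

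- *Early stoppers.* Section 9.3 puts anyone who took one dose in the modified intention-to-treat set. Section 9.4.2 fits acute and chronic effects separately, and both acute scans are at Visit 2. Section 7.1 says that stopping the intervention means leaving the study. Someone who stops after Visit 2 can therefore have complete acute data and be in the set, with no DNA draw planned for them. Replacing that person under section 7.2 does not take them out of the set.
- *Completers who do not return.* They have full acute and chronic data and no genotype.

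One limit applies to the first group. If section 9.3.2 is read as requiring all four listed measures after baseline, an early stopper is not evaluable for response, because outcome cognitive testing is repeated only at Visit 4. The plan does not say which set governs the genetic model. The second group is affected on either reading.

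**4. Size.** Let r be the Visit 5 return rate among 50 completers and f the share in the smaller genotype group. Neither is in the documents; both are assumptions. With n = 25r per arm:

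- number genotyped = 50r
- standard error factor = √(1/r)
- variance of the Group-by-genotype contrast, in SD units = 2/(nf) + 2/(n(1 − f)), tested by noncentral t on 2n − 4 df

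For f = 0.25 and r = 1 the variance is 2/6.25 + 2/18.75 = 0.427 (SE 0.653). At r = 0.8 it is 2/5 + 2/15 = 0.533 (SE 0.730), a ratio of 1.12.

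| r | Genotyped | SE factor | Smaller group per arm (f = 0.25) | Interaction detectable at 80% power | Power for 0.8 SD |
|---|---|---|---|---|---|
| 1.0 | 50 | 1.00 | 6.25 | 1.87 SD | 0.22 |
| 0.9 | 45 | 1.05 | 5.6 | 1.98 SD | 0.21 |
| 0.8 | 40 | 1.12 | 5.0 | 2.10 SD | 0.19 |
| 0.7 | 35 | 1.20 | 4.4 | 2.26 SD | 0.17 |

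Over f = 0.20 to 0.50, the detectable interaction is 2.02 to 1.62 SD at r = 1.0 and 2.28 to 1.82 SD at r = 0.8.

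**5. Does Visit 5 count towards completion?** The payment of $1100 for completing the study equals 50 + 300 + 200 + 500 + 50, so it includes Visit 5. Section 7.3 treats Visit 4 as final. The two do not agree.

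**The case against.** The strongest reply is that APOE and SLC16A7 genotypes are fixed, so a late or undated draw gives the same value as an early one. That stands. A reader might infer that late sampling distorts the genotype data; it does not. Only missingness and selection remain.

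The selection is possible rather than shown. No section says that return depends on tolerability or benefit, and Visit 5 is paid ($50), which favours return. People with poor tolerance mostly leave before Visit 5, so among completers the selection may be mild. The same early departure, though, is what leaves early stoppers without a genotype.

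The endpoint is also underpowered with or without this problem: 0.22 against 0.19 for a 0.8 SD interaction at 80% return. That stands too. Loss at Visit 5 is not the cause of the low power.

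Two stronger readings are tempting and not supported:

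- *That methylation measured after treatment will be used as an effect modifier.* Methylation appears once, in the section 2.3.1 risk item on genetic testing ("genotyping for APOE and other modulatory genes; DNA methylation"). It is not in the endpoint, section 9.4.3 or the SAP, so no such analysis is planned.
- *That anyone who skips Visit 5 is lost to follow-up and replaced.* The opening sentence of section 7.3 invites this, but the section treats a person as withdrawn only if they stay unreachable after repeated contact attempts, and it covers rescheduling for Visits 1 to 4 only. A completer who declines Visit 5 is reachable. This is an ambiguity, not a stated rule.

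Finally, the separate consent would fit a recall visit added late. The documents do not give enrolment status, so this cannot be settled from them. If it is so, moving the draw helps only people still to come.

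**Conclusion.** The concern holds as a design weakness that is cheap to avoid. The only secondary endpoint rests on one sample, taken at a visit that dosed participants can miss for reasons arising after randomisation, and no rule covers those who miss it. The consequence is avoidable missing genotypes and possible selection.

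The loss of precision is modest over the range shown: standard errors about 5% to 20% wider for an assumed 90% to 70% return. These figures cover non-return among completers only; early stoppers come on top if the genetic model uses the modified intention-to-treat set. The amount and direction of any selection bias cannot be worked out from the documents.

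**What to change.** - **Not yet at Visit 2:** obtain genetic consent at Visit 1 and draw the 8-10 ml DNA tube with the Visit 2 pre-dose blood.
- **Between Visits 2 and 4:** obtain the consent and draw the tube at the next scheduled visit.
- **Already finished:** keep Visit 5 as a recall visit and give it a window.
- **Section 9.4.3 and the SAP:** define the analysis set for the genetic models and report numbers genotyped by arm, with reasons for missing DNA.
- **Minor clarification:** reconcile sections 7.2 and 7.3 with the completion payment in section 5.6.2, so that missing Visit 5 does not make a person with complete primary data lost to follow-up or replaced.
- **Methylation:** if it is analysed at all, do not use a post-treatment value as a modifier of the treatment effect.

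The cost is a consent and schedule amendment and 8-10 ml more blood. The Visit 2 maximum would rise from 40 ml to 48-50 ml, below the 55 ml already allowed at Visit 4. For future participants the change removes a visit, its meal and its $50 payment. Refusals of genetic consent would remain, and nothing is gained for people who have already completed.
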